4.2.3. PK/PD Expansion Cohorts

Any dose level(s) in Part 1 may be expanded up to 12 subjects in order to collect adequate data on safety, PK or PD. However, PD sample (peripheral blood and bone marrow aspirate) collection may be stopped early at the sponsor's discretion. Subjects may be enrolled at previously completed dose levels for the purpose of obtaining additional data. These subjects may have the dose escalated to a higher completed dose level (not exceeding the maximum tolerated dose [MTD]) once the necessary PK/PD procedures have been completed.

4.2.4. Alternative Dosing and PK/PD Sampling Schedules

In Part 1 Dose Escalation phase, subjects will initially receive daily dosing of GSK2879552. If the terminal half-life is longer than 5 hours, some subjects may be requested to withhold Day 2 and Day 3 dosing to obtain blood samples for PK analysis at timed intervals up to 72 hours after dosing. Once their final PK sample on Day 4 is obtained, these subjects would begin repeat dosing on Day 4. In Part 2, subjects will begin repeat dosing per RP2D and regimen from Day 1.

Further alterations may be made to the dosing schedule and/or PK/PD sampling schedule of GSK2879552 or ATRA based on the results of emerging PK, PD, efficacy and safety data, and documented in the SPM. These changes will be communicated to IRB/EC, but would not constitute a protocol amendment.

Schedules that incorporate a recovery period may be explored (e.g., 4 days on/3 days off). Alternatively, a drug holiday after continuous dosing may be explored for GSK2879552 and/or ATRA. This approach may be considered if higher exposure is desired for an improved clinical activity (i.e., higher response rate) or therapeutic exposure cannot be achieved without excessive toxicity. If MTD was not exceeded with the initial schedule, the starting dose for the alternate schedule will be the one dose level higher than the highest completed dose level. If MTD was exceeded with the initial schedule, the starting dose for the alternate schedule will be no higher than the highest tested daily dose.

4.2.5. Dose-Limiting Toxicity

An event will be considered a DLT if it occurs within the first 28 days of treatment (with exception of myelosuppression as stated below), and meets one of the following criteria unless it can be clearly established that the event is unrelated to treatment.

Subjects unable to receive at least 75% of scheduled doses within the DLT period for reasons other than toxicity (e.g., acute illness, disease progression) will not be evaluable

- Hematologic DLT: Myelosuppression (as defined by absolute neutrophil count (ANC) $<500/\mu\text{l}$ AND platelets $\leq 25,000/\mu\text{l}$) with bone marrow hypoplasia (cellularity $\leq 5\%$) without evidence of leukemia ($<5\%$ blasts) for ≥ 42 days after drug cessation.
- Grade ≥ 3 non-hematologic toxicity that is considered clinically significant and lasts >72 hours. Fatigue, asthenia, or nausea that respond to standard medical care within 72 hours and new electrolyte disturbance that respond within 24 hours are exceptions. In addition, electrolyte disturbances associated with underlying malignancy are not considered DLT.
- Grade 2 toxicity that in the judgment of the investigator and GSK Medical Monitor is dose-limiting.
- Treatment delay of ≥ 42 days due to unresolved toxicity (without evidence of leukemia ($<5\%$ blasts)).

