1.3.5. Clinical Safety of GSK2879552

Summary of findings from clinical studies conducted with GSK2879552 can be found in the Investigator Brochure for GSK2879552 [GlaxoSmithKline Document Number [2013N168888_03](#)].

As of 20-NOV-2015, 11 subjects have been enrolled in Part 1 at once daily doses of 1 mg (n=1), 2 mg (n=2), 4 mg (n=7), and 8 mg (n=1). All 11 subjects (100%) had experienced AEs. The most frequently reported AEs (>20%) were fatigue, febrile neutropenia, nausea, anemia, decreased appetite, hypotension, rash, cellulitis, hypokalemia, and local edema. All Grade 4 AEs were hematological and included thrombocytopenia and neutropenia. Treatment-related AEs reported in at least 10% of subjects were nausea, decreased appetite, and thrombocytopenia. The treatment-related thrombocytopenia AEs were Grade 4 in both subjects; one of these subjects also had Grade 3 febrile neutropenia and Grade 3 anemia. Other treatment-related events that were Grade 3 or 4 included anemia and nausea. There were no fatal AEs.

All 11 subjects in Study 200200 have experienced SAEs. The most common SAE was febrile neutropenia. All cases of febrile neutropenia resolved. No other SAEs occurred in more than 1 subject. One subject had fatal pleural effusion secondary to disease under study, which was considered by the investigator to be not related to study treatment.

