- No subjects treated at next higher dose level have toxicity meeting the above criteria.

However, the dose escalation may continue with multiple subjects per cohort per the clinical judgment of the Medical Monitor and internal dose-escalation committee in consultation with the investigators. The decision on the number of subjects will be documented in writing together with the dose escalation decision and the rationale.

Maximum Dose Increment

Built-in safety constraints are in place to prevent exposing subjects to undue risk of toxicity. The dose increment will be no more than 100% of the current dose in the absence of any safety signals. The dose increment will be no more than 50% of the current dose after DLT or any Grade 2 or higher non-hematologic adverse event that is considered related to the study medication (with the exceptions as above) is observed. The maximum allowable dose increment will be determined based on the prior dose level data.

Completion of Dose Escalation

The dose escalation will complete when MTD and/or RP2D is determined. The RP2D will be the MTD or a lower dose that provides adequate PK exposure and biologic activity with superior tolerability. The identification of MTD may not be necessary if a clear RP2D emerges without reaching the MTD. The final determination of RP2D will be based on the N-CRM suggested dose level, or the biologically active dose (e.g., clinical response), the safety profile, and available PK and PD data generated from all subjects in Part 1. Up to 12 additional subjects will be enrolled at the dose to further define the safety and tolerability of the dose and schedule. If necessary, alternate schedules can be explored to determine additional biologically active doses even after a RP2D is defined.

Dose Escalation Committee

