4.4. Intra-subject Dose-Escalation

Intra-subject dose escalations may be considered on a case-by-case basis, provided that the subject has not experienced a DLT, and a higher dose level cohort has been cleared without a DLT.

Decision on intra-subject dose escalation will be made after review of all safety data and approval by a GSK Medical Monitor and discussion with the investigator.

Subjects approved for intra-subject dose escalation will require additional limited PK sampling at the higher dose as determined by GSK Clinical Pharmacology.

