4.8.2. Dose Adjustment for Non-Hematologic Toxicity

See [Table 2](#) Dose Adjustment Guideline for drug related non-hematologic toxicities based on worst grade.

Table 2 Dose Adjustment Guideline for Drug Related Non-Hematologic Toxicity

Worst Grade	Dose Adjustment
G1	No change in dose
G2 [†]	Continue dosing with no change OR Consider holding for up to 2 weeks for toxicity to resolve to baseline or ≤ Grade 1, then continue at the same dose OR dose reduce by at least 25% if the toxicity is considered a DLT.
G3 and 4 [†]	Hold for up to 2 weeks for toxicity to resolve to baseline or ≤ Grade 1, then dose reduce by at least 25%. If no recovery to ≤Grade 1* or baseline after 14 days, patient should be withdrawn.

*Note: Exceptions to ≤ drug-related Grade 1 requirement may be made for rash, alopecia, quickly reversible (<72 hours) laboratory abnormality (example: electrolyte changes).

[†]In combination cohort, consider holding ATRA dosing first for skin related toxicity (dryness, rash), nausea, vomiting, pain, headache, and mucositis. With fever, consider holding LSD1 first to allow neutrophil count to recover.

If the non-hematologic toxicity or event resolves to baseline or ≤ Grade 1 within 14 days of stopping therapy, treatment with GSK2879552 and/or ATRA may be restarted with at least **25%** dose reduction. For a non-DLT, the treatment with GSK2879552 could restart at a full dose, if deemed appropriate.

If the non-hematologic toxicity does not resolve to ≤ Grade 1 or baseline within 14 days, the subject should be withdrawn from the treatment permanently (Section 6.3). However, if the investigator and GSK Medical Monitor agree that further treatment will benefit the subject, treatment can restart with at least **25%** dose reduction once the toxicity resolves to ≤ Grade 1 or baseline.

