Dose level	GSK2879552 ATRA <30mg/m²
1a	2 mg/day
-1a	1 mg/day
-2a	0.5 mg/day

Dose level 1: GSK2879552 2 mg/day

Dose level 2: GSK2879552 4 mg/day

Dose level 3: GSK2879552 8 mg/day

Dose level 4: GSK2879552 16 mg/day

Dose level 5: GSK2879552 32 mg/day

Section 4.2.5: Dose-Limiting Toxicity

Rationale for change: The text was updated to clarify criteria for a DLT.

REVISED TEXT:

Second paragraph, first sentence:

An event will be considered a DLT if it occurs within the first ~~4 weeks~~ 28 days of treatment (with exception of myelosuppression as stated below), and meets one of the following criteria unless it can be clearly established that the event is unrelated to treatment.

Subjects unable to receive at least 75% of scheduled doses within the DLT period for reasons other than toxicity (e.g., acute illness, disease progression) will not be evaluable

Hematologic DLT:

- Myelosuppression (as defined by absolute neutrophil count (ANC) <500/ μ l AND platelets \leq 25,000/ μ l) with bone marrow hypoplasia (cellularity \leq 5%) without evidence of leukemia (<5% blasts) for \geq ~~28~~ 42 days after drug cessation. ~~If a subject meets above criteria at the time of drug cessation within the DLT observation period, the dose escalation decision will be delayed until 28 days have elapsed post drug cessation.~~

- Grade ≥ 3 ~~or 4~~ non-hematologic toxicity that is considered clinically significant and lasts >72 hours. Fatigue, asthenia, or nausea that respond to standard medical care within 72 hours and new electrolyte disturbance that respond within 24 hours are exceptions. In addition, electrolyte disturbances associated with underlying malignancy are not considered DLT.
- Grade 2 toxicity (~~at any time during treatment~~) that in the judgment of the investigator and GSK Medical Monitor is dose-limiting.
- Treatment delay of ≥ 42 ~~28~~ days ~~or greater~~ due to unresolved toxicity.

Section 4.7.3: Mental Status Stopping Criteria

Rationale for change: Clarify the definition of «baseline» MOCA.

REVISED TEXT:

Second paragraph, second bullet:

- A decrease of 3 points or more from baseline (Pre-dose Day 1) MOCA score

Third paragraph, first bullet:

- A reversible cause other than study treatment is identified and both MOCA score and symptoms return to baseline or to the MOCA score before the decrease.

Section 4.8.3: Dose Adjustment for Hematologic Toxicity

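### A Grade 4 non-hematologic toxicity that resolves within 72 hours meets no DLT criterion in Section 4.2.5, so the dose-escalation model counts it as no DLT

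*Protocol*

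**What the plan says.** Protocol Section 4.2.5 lists four ways to have a DLT in the first 28 days, each applying unless the event is clearly unrelated to treatment:

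- prolonged myelosuppression with a hypoplastic marrow;
- a Grade 3 or higher "non-hematologic toxicity that is considered clinically significant and lasts >72 hours", with exceptions for some fatigue, asthenia, nausea and electrolyte events;
- a "Grade 2 toxicity that in the judgment of the investigator and GSK Medical Monitor is dose-limiting";
- a treatment delay of at least 42 days for unresolved toxicity.

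Two subject-level rules depend on DLT status. In Section 4.8.2, the Grade 3 and 4 row of Table 2 advises holding the drug until a related toxicity is back to baseline or no worse than "Grade 1, then dose reduce by at least 25" percent. The text under the table adds: "For a non-DLT, the treatment with GSK2879552 could restart at a full dose, if deemed appropriate". Section 4.4 allows intra-subject escalation "provided that the subject has not experienced a DLT, and a higher dose level cohort has been cleared without a DLT", after review of all safety data and Medical Monitor approval.

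Other safeguards do not depend on DLT status. Section 4.2.1 states: "The dose increment will be no more than 50% of the current dose after DLT or any Grade 2 or higher non-hematologic adverse event" considered related to study drug. Such an event also triggers larger cohorts, and the committee reviews non-DLT toxicities and may halt, reduce or reverse escalation.

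**The concern.** The duration condition covers every grade from 3 upward, so a life-threatening event that is brought under control in two days is treated like a brief Grade 3 event. The judgement clause cannot rescue it, because that clause names Grade 2 only. The investigator and Medical Monitor can call a Grade 2 toxicity dose-limiting but have no stated route to do so for a short Grade 4 toxicity.

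What is at stake is the meaning of the DLT rate. The N-CRM and the MTD definition in Section 4.2.6 use DLTs as Section 4.2.5 defines them, so an estimated rate inside the 16% to 33% target interval would not include brief Grade 4 non-hematologic toxicity. The affected subject also remains, on paper, a candidate for full-dose restart and for a higher dose.

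**Working it through.** The plan states no figure on this point, so there is nothing to reproduce first. The check has four steps.

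**1. The event against each criterion.** Take a clinically significant Grade 4 non-hematologic event on day 10 that resolves in 48 hours and is not clearly unrelated to treatment.

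| Section 4.2.5 criterion | Met? | Reason |
|---|---|---|
| Hematologic | No | The event is non-hematologic |
| Grade 3 or higher, significant, over 72 h | No | 48 h is less than 72 h |
| Grade 2 by judgement | No | The event is Grade 4 |
| Delay of 42 days or more, unresolved | No | The event has resolved |

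None of the four is met.

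**2. What follows from non-DLT status.** The model receives a zero for this subject. The non-DLT sentence in Section 4.8.2 applies, and the no-DLT condition in Section 4.4 is satisfied for the subject.

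**3. How often it might occur.** Protocol Section 1.3.5 reports on 11 subjects as of 20 November 2015: "All Grade 4 AEs were hematological and included thrombocytopenia and neutropenia". That gives 0 of 11 with a Grade 4 non-hematologic event of any duration. The one-sided 95% upper limit is 1 − 0.05^(1/11) = 0.238, or 24% of subjects. The documents give no durations.

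**4. What one event does to the model (monotherapy illustration).**

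- Model: logit p(d) = α + β ln(d/5), with the 5 mg reference dose from Section 4.2.1.
- Prior from Appendix 1 (mean, SD): α −1.6278 (1.3652), ln β −0.0116 (0.4136), correlation 0.2429. The posterior was computed on a grid of ±6 SD.
- Data: the Table 6 counts of 0/1, 0/2 and 0/4 at 1, 2 and 4 mg, plus n subjects at the event dose, one of whom has the event.
- Rule: among the Table 1 doses, choose the highest posterior probability of a DLT rate in [16%, 33%), provided P(rate ≥ 33%) is below 0.25. The event is assumed related, so the 50% cap applies whether or not it is counted.

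Example 1: event at 8 mg. Cap 8 × 1.5 = 12 mg.

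| n at 8 mg | P(rate ≥ 33%) at 12 mg, uncounted / counted | Next dose, uncounted / counted |
|---|---|---|
| 2 | 0.14 / 0.44 | 12 / 6 mg |
| 3 | 0.11 / 0.36 | 12 / 8 mg |
| 4 | 0.08 / 0.30 | 12 / 10 mg |
| 5 | 0.06 / 0.24 | 12 / 12 mg |

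Example 2: 0/1 at 8 mg, event at 12 mg. Cap 12 × 1.5 = 18 mg, so 15 mg is the highest available Table 1 dose.

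| n at 12 mg | P(rate ≥ 33%) at 15 mg, uncounted / counted | Next dose, uncounted / counted |
|---|---|---|
| 2 | 0.13 / 0.43 | 15 / 10 mg |
| 3 | 0.09 / 0.34 | 15 / 12 mg |
| 4 | 0.07 / 0.26 | 15 / 12 mg |
| 5 | 0.05 / 0.21 | 15 / 15 mg |

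More clean data at 8 mg shrinks the effect in Example 2. With 0/3 there, the next dose changes only with 1 or 2 subjects at 12 mg; with 0/6, only with 1.

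**The case against.** The strongest reply is that the DLT label is only one input. The N-CRM recommends and the committee decides, having seen non-DLT toxicities. A related event enlarges cohorts and halves the permitted increment. Liver, QTc and mental-status stopping rules act whatever the DLT status. All of this stands and limits the harm. It does not put the event into the model, and the 50% cap is already inside the calculations above.

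A reader might infer that Table 2 mandates a 25% reduction and so contradicts Section 4.2.5. The documents do not support that. Table 2 is a guideline, and the non-DLT sentence beneath it softens the reduction for exactly this kind of event. DLT status and individual dose modification also serve different purposes, and a brief Grade 3 event would show the same difference even after the fix below. The table is context only.

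A reader might also infer a drafting slip, because Appendix 10 shows the duration condition arriving with Amendment 5 under the rationale "The text was updated to clarify criteria for a DLT". A difference from superseded text is not an error, and the amendment's summary speaks of optimizing the DLT criteria, which suggests a deliberate choice. The case for change rests on the current wording alone.

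Finally, nothing shows that such an event occurred. SAP Section 5.1 lists 20 mg as the next monotherapy level after 12 mg, a step of 8/12 = 67%. If the levels were used in that order and the cap was applied, no related triggering event was seen at 12 mg, and Example 2 did not arise.

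**Conclusion.** The gap is real and follows directly from the wording of Section 4.2.5. Closing it is a cheap improvement; it does not correct a demonstrated mistake in a dosing decision. The MTD is consistent with DLTs as the protocol defines them, so the documents do not support a claim that it is invalid or set too high. What can be said is that the DLT rate behind it leaves out brief Grade 4 non-hematologic toxicity.

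The size is hypothetical. In the illustrations, the model's next dose changes only with about four or fewer subjects at the event dose. Section 4.2.1 allows monotherapy cohorts of one subject, or a minimum of two after a toxicity trigger, so small numbers are realistic. The figures assume one related event, the Appendix 1 prior and the Table 6 counts. They do not reconstruct actual decisions, and they model neither committee judgement nor the combination arm.

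**What to change.** Reword the second bullet of Section 4.2.5 so that the 72-hour allowance applies to Grade 3 only. Count as a DLT, whatever its duration, any clinically significant Grade 4 non-hematologic event, except an asymptomatic and quickly reversible laboratory value, and any Grade 5 event, in each case unless clearly unrelated to treatment. Sections 4.4 and 4.8.2 then give the intended result for these events without further edits. The cost is one bullet and slightly slower escalation: in Example 1 with three subjects, the next cohort is treated at 8 mg instead of 12 mg.

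SAP Section 2.1 records that the study was terminated early and Part 2 never opened, so the amended wording serves any later protocol that reuses these criteria. For this report, flag every Grade 4 or 5 non-hematologic event in days 1 to 28 that was excluded as a DLT on duration alone; the flag can be added to SAP Listing 15, which already covers all adverse events. If there are none, one sentence saying so is enough. If there are any, rerun the model with them counted and report both results.

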1.4.5.1. Risk Assessment

Potential Risk of Clinical Significance	Data/Rationale for Risk	Mitigation Strategy
Lymphoid/hematologic and associated bleeding and infection risks	The primary toxicity with GSK2879552 is a dose-dependent mild-to-severe thrombocytopenia, observed in mice, rats and dogs. Reduced platelet aggregation has been observed in rats following repeat dosing at a time when there was significant thrombocytopenia. A dose-dependent mild-to-severe neutropenia was observed in rats, but not dogs, and was not associated with systemic infections. Mild effects on the erythron were observed in rats and dogs which may reflect both a direct and indirect (i.e., secondary to bleeding/hemorrhage) effect on the erythroid lineage. In general, hypocellularity was not observed in the bone marrow of these animals.	
Informed Consent Form includes the risk of hematologic toxicity.
 
Protocol specifies:
 
 - Exclusion criteria for non-AML related major bleeding (e.g. recent GI hemorrhage or neurosurgery) - Laboratory assessments (complete blood count [CBC]) - Dose stopping/modification criteria 
Signs and symptoms of bleeding or infection will be closely monitored during the study.

Encephalopathy	Three (out of 18) subjects enrolled in 200858 study experienced encephalopathy.	
Informed Consent Form is updated to include the risk of mental status change.
 
Protocol eligibility and monitoring criteria are modified:
 
 - subjects who have received prior treatment with temozolomide, dacarbazine, procarbazine, or PARP inhibitors are excluded - Subjects should have baseline thyroid function, vitamin B12 level and metabolic panel within acceptable limits - Montreal Cognitive Assessment (MOCA) at baseline and weekly for the first 4 weeks and monthly thereafter. - Subjects with baseline MOCA score of ≤ 22 are excluded 
Protocol stopping criteria is modified:
 
 - Dosing will be held and neurology consult will be required if a decrease of 3 points or more from baseline MOCA score or any score of < 22 occurs or in case of any other indication of early encephalopathy as determined by patient history or physical exam

Potential Risk of Clinical Significance	Data/Rationale for Risk	Mitigation Strategy
ATRA Combination ONLY		

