4.7.3. Mental Status Stopping Criteria

Enrollment will be stopped upon the occurrence of any encephalopathy, unless clearly attributable to central nervous system disease involvement or intercurrent illness.

Study treatment will be held and neurology consult obtained if any of the 3 criteria below are met:

- A decrease of 3 points or more from baseline (Pre-dose Day 1) MOCA score
- Any MOCA score of <22
- Any other indication of early encephalopathy as determined by patient history or physical exam

The treatment may resume if one of the following criteria is met:

- A reversible cause other than study treatment is identified and both MOCA score and symptoms return to baseline or to the MOCA score before the decrease.
- Evaluated by a neurologist and found to have no clear signs/symptoms of encephalopathy or other cognitive dysfunction. This is applicable only in the absence of decrease in MOCA score.

All treatment restarts must be approved by GSK medical monitor.

The treatment should be permanently discontinued for subjects with documented symptoms with no other cause, even if they return to baseline.

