6.3. Permanent Discontinuation from Study Treatment

Subjects will receive study treatment until disease progression, death or unacceptable toxicity, including meeting stopping criteria for liver chemistry defined in Section 4.7.1. The investigator may discuss with a GSK Medical Monitor continuing a subject who is receiving benefit but has met the criteria for disease progression, if the following criteria are met: Investigator-determined clinical benefit (e.g. symptomatic improvement), lack of

significant toxicity (no drug related non-hematologic grade 3/4 AEs within the last 4 weeks) and no therapeutic alternatives expected to provide durable responses.

In addition, study treatment may be permanently discontinued for any of the following reasons:

- Deviation(s) from the protocol
- Request of the subject or proxy (withdrawal of consent by subject or proxy)
- Investigator's discretion
- A clinically significant hematologic adverse event leading to an interruption of treatment for greater than 28 days. Subjects will be allowed up to a 28-day delay in dosing for hematologic toxicity to resolve or for scheduling difficulties. If the investigator and GSK Medical Monitor conclude that the benefit: risk supports continued treatment of a subject who has had a > 28 day treatment delay, then the subject may continue therapy with the approval of the GSK Medical Monitor.
- A clinically significant non-hematologic adverse event leading to an interruption of treatment for greater than 14 days. Subjects will be allowed up to a 14-day delay in dosing for non-hematologic toxicity to resolve or for scheduling difficulties. If the investigator and GSK Medical Monitor conclude that the benefit: risk supports continued treatment of a subject who has had a > 14 day treatment delay, then the subject may continue therapy with the approval of the GSK Medical Monitor.
- Persistent G4 thrombocytopenia for 4 weeks not attributed to disease or requires platelet transfusions for bleeding in the absence of the disease.
- Intercurrent illness that prevents further administration of study treatment(s)
- Subject is lost to follow-up
- Study is closed or terminated.

The primary reason study treatment was permanently discontinued must be documented in the subject's medical records and electronic case report form (eCRF).

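### Protocol 4.2.5 does not say how a subject stopped or under-dosed by toxicity is counted in the N-CRM, and its 42-day delay criterion conflicts with the 28-day DLT window and the stopping limits elsewhere

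*Protocol*

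**What the plan says.** **DLT definition (Protocol 4.2.5).** The window is 28 days: "An event will be considered a DLT if it occurs within the first 28 days of treatment (with exception of myelosuppression as stated below". Subjects who cannot take 75% of scheduled doses "for reasons other than toxicity (e.g., acute illness, disease progression) will not be evaluable". The replacement rules in 4.2.1, 4.2.2 and SAP Appendix 7 make the same distinction. There are four criteria:

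- ANC <500/µl and platelets ≤25,000/µl, with marrow cellularity ≤5% and <5% blasts, for at least 42 days off drug;
- Grade ≥3 non-hematologic toxicity that is clinically significant and lasts more than 72 hours, with listed exceptions;
- Grade 2 toxicity that the investigator and Medical Monitor judge dose-limiting;
- a treatment delay of at least 42 "days due to unresolved toxicity (without evidence of leukemia" (<5% blasts).

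**Stopping limits elsewhere.**

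- 4.8.2, Table 2, Grade 3-4 row: if there is no recovery to Grade 1 "or baseline after 14 days, patient should be withdrawn". The text below the table applies 14 days to non-hematologic toxicity generally, with a Medical Monitor exception.
- 6.3: treatment may be discontinued for "A clinically significant hematologic adverse event leading to an interruption of treatment for greater than 28 days", for a non-hematologic interruption beyond 14 days, or for Grade 4 thrombocytopenia persisting 4 weeks and not attributed to disease. The 14- and 28-day delays carry Medical Monitor exceptions.
- 4.8.3, row for blasts below 5%: holding can run to 5-6 weeks, with a marrow check at about day 35-42 off drug and withdrawal at 6 weeks.

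The SAP adds no rule on how these subjects are counted.

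**The concern.** The evaluability rule and the DLT criteria do not fit together. Toxicity keeps an under-dosed subject in the denominator, but nothing makes stopping for toxicity, or falling below 75% of doses because of it, a DLT unless another criterion happens to be met. The model then treats a subject with perhaps half the planned exposure as a full observation of tolerability. The same toxicity could also be scored differently according to whether the subject was held to day 42 or withdrawn earlier.

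DLTs are part of the Part 1 primary endpoint, the only outcome the N-CRM uses, and the basis of the MTD definition in 4.2.6. Thrombocytopenia is where this matters most. Section 1.4.5.1 calls it the primary toxicity, yet the hematologic DLT needs marrow hypoplasia, and the same section says of the animal studies: "In general, hypocellularity was not observed in the bone marrow of these animals". Section 1.3.5 reports treatment-related thrombocytopenia in two of 11 subjects: "The treatment-related thrombocytopenia AEs were Grade 4 in both subjects".

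**Working it through.** **1. Day counts.** 75% of 28 daily doses is 0.75 × 28 = 21. A hold of 8 days inside the window leaves 20/28 = 71%, below the threshold. A 14-day hold inside the window leaves 14/28 = 50%. A subject held from Day 8 and then withdrawn has taken 7/28 = 25%. If the cause is toxicity, all three remain evaluable.

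**2. The delay criterion against the window.** 42 > 28, so a 42-day delay cannot be completed inside the window even if it starts on Day 1. The only stated exception to the window is myelosuppression. Read literally, a delay for any other toxicity cannot qualify in time.

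**3. The delay criterion against the stopping limits.**

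| Provision | Limit | Days short of 42 |
|---|---|---|
| 4.8.2 and 6.3, non-hematologic | 14 days | 28 |
| 6.3, hematologic interruption | more than 28 days | about 14 |
| 6.3, persistent Grade 4 thrombocytopenia | 4 weeks | 14 |
| 4.8.3, blasts below 5% | 6 weeks | 0 |

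Only the last row reaches 42 days without a Medical Monitor exception or a discretionary choice not to discontinue, and it contradicts the 4 weeks in 6.3.

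**4. Who falls through.** A clinically significant Grade ≥3 non-hematologic event unresolved at 14 days has already exceeded 72 hours, so it is already a DLT. What remains is:

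- isolated Grade 4 thrombocytopenia or neutropenia that stops dosing;
- Grade 2 events unresolved at 14 days but not judged dose-limiting;
- Grade ≥3 events that are brief or judged not clinically significant but still cost doses.

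For the first group, the 50% cap on dose increments in 4.2.1 does not respond either. Its triggers are a DLT or a related non-hematologic event of Grade 2 or higher.

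**5. Sensitivity of the model (illustration).** Inputs:

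- Model: logit P(DLT at dose d) = α + β·ln(d/5), with reference dose 5 mg (4.2.1).
- Prior (Appendix 1): α mean −1.6278 (SD 1.3652), ln β mean −0.0116 (SD 0.4136), correlation 0.2429.
- Data (Table 6): 0/1, 0/2, 0/4 and 0/1 at 1, 2, 4 and 8 mg.
- Rule (4.2.1): the dose with the highest P(16% ≤ rate < 33%) among those with P(rate ≥ 33%) < 0.25, subject to the increment cap.

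Results by grid integration:

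| Data | Recommended dose | P(rate ≥ 33%) there | Next dose up |
|---|---|---|---|
| Table 6 as given | 15 mg | 0.247 | 20 mg: 0.335 |
| One of four at 4 mg recoded as DLT | 6 mg | 0.175 | 8 mg: 0.290 |
| The 8 mg subject recoded as DLT | 6 mg | 0.208 | 8 mg: 0.347 |

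15 mg is within the 100% cap from 8 mg (16 mg). With three hypothetical further subjects at 12 mg added to Table 6, P(rate ≥ 33%) at 12 mg is 0.053, 0.237 or 0.553 for zero, one or two counted DLTs.

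The documents give no figure to reproduce here. The Appendix 1 prior has median 1/(1 + e^1.6278) = 0.164 at 5 mg, against 0.10 in Table 1, so it fits Table 1 only approximately. The argument in steps 1-4 does not depend on it.

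**The case against.** **The hematologic definition is deliberate.** Section 1.4.3.2 explains that AML subjects start with disease-suppressed marrow, so only prolonged suppression is counted. That stands. A reader might infer that isolated Grade 4 thrombocytopenia ought to be a DLT. The documents do not establish that, and it is not claimed here.

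**The 42-day criterion is reachable.** It is limited to subjects without leukemia, and the blasts-below-5% row of 4.8.3 leads to that point and orders a marrow for the purpose. That stands for the cases 4.8.3 covers. It leaves the clash with 6.3 and, for other toxicities, with the window.

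**Encephalopathy.** A reader might infer that low-grade encephalopathy slips into the model as DLT-free, because 4.7.3 says: "The treatment should be permanently discontinued for subjects with documented symptoms with no other cause, even if they return to baseline". But the same section opens by stopping enrollment on any encephalopathy not clearly due to CNS disease or intercurrent illness, with no grade limit. Escalation does not simply continue.

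**Other safeguards.** Related Grade ≥2 non-hematologic events, with exceptions, enlarge cohorts and cap increments. The dose-escalation committee reviews non-DLT toxicities and dosing logs and can halt or reduce escalation. Dose reductions, delays and withdrawals are also primary endpoints, and the RP2D may be set below the MTD. These limit the practical harm. They do not change the model's input or the posterior that defines the MTD.

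**Scoring every such subject as a DLT has its own risk.** All 11 subjects in 1.3.5 had SAEs, and attribution in AML is often unclear. A blanket rule could push the MTD down, possibly below the 10-40 mg predicted to be effective. That is why showing both counts is preferable to prescribing one.

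**Conclusion.** The gap is real but narrower than the day counts alone suggest. As written, a subject withdrawn or under-dosed for toxicity can be a full DLT-free observation, mainly for isolated Grade 4 cytopenia or a Grade 2 event not judged dose-limiting. Classification can also depend on whether the subject was held or withdrawn. Most Grade ≥3 non-hematologic events are already captured.

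Where such a subject occurs, the possible effect is an MTD estimate that is too high, and with so few subjects one classification matters. The 15 mg to 6 mg shift shows that sensitivity and nothing more. A reader might infer that the trial's own MTD estimate was biased, or that the two Grade 4 thrombocytopenia subjects were miscounted. The documents do not support either: Section 1.3.5 gives neither their dose levels nor whether they stopped dosing, and nothing shows that they are among the eight in Table 6. The SAP's list of dose groups also has 12 mg, not 15 mg, after 8 mg.

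The conclusion assumes that 4.2.5 is applied as written and that no counting rule exists outside these two documents. Early termination does not remove the point, since the SAP keeps DLTs in the Part 1 primary endpoint.

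**What to change.** 1. Reconcile 4.2.5, 4.8.2, 4.8.3 and 6.3: the 42-day delay criterion against the 28-day window and the 14- and 28-day limits, and 4 weeks against 6 weeks for persistent Grade 4 thrombocytopenia. Which limit applies is for the sponsor's clinicians.
2. State in 4.2.5 and the SAP how the model enters a subject who discontinues, or receives under 75% of doses in the first 28 days, because of toxicity.
3. At each escalation decision and in the study report, list these subjects by dose with the doses received. Show the N-CRM posterior twice, with them as DLT-free and as DLTs.

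The cost is a short amendment and one extra model run per decision. With the study terminated, a clarification and a sensitivity display in the abbreviated report would serve. The downside is a little more analysis and, while escalation is running, possibly a slower pace.
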